7.2.1 Plasma Exchange

The percentage of plasma exchanges (full and low volume exchanges, including the infusion of albumin and IVIG) associated with at least one adverse event that may be related to the study procedure (adverse reactions) will be summarized. Only adverse events with an onset no later than 72 hours after the end of the plasma exchanges (including the infusion of albumin or IVIG) will be considered for this analysis.

Plasma exchanges (full and low volumes exchanges) will also be summarized by the following measures:

- Plasma exchange performed (yes/no)
- Duration of plasma exchange
- Plasma exchange completed (yes/no)

The reasons for not completing the plasma exchanges will be presented in a data listing.

For the full plasma exchanges, also the following measures will be summarized:

- Route to perform full plasma exchange (peripheral / central)
- Number of bottles of albumin used (calculated as numbers of bottles in this batch + all additional bottles).
- Plasma volume exchanged (ml)

	Title: Statistical Analysis Plan
	Project #: IG1002 AMBAR
	Version: Final 1.0 Effective Date: 31July2018
	Protocol Version: Version 5.0 Effective Date: Feb2018

- Volume RF infused (ml)

For the low volume plasma exchange, the following parameters will be summarized:

- Target plasma volume
- Target RF volume
- Type of RF used (20% HAS, Other)
- RF infused
- Plasma volume exchanged (calculated as $[(PPP_{\text{post weight}} - PPP_{\text{bag empty}}) / 1.027 \text{ g/ml}] \text{ ml}$ where $PPP_{\text{bag empty}} = 41.87\text{g}$)
- Number of bottles Albumin used

For the plasma exchange visits where IVIG are to be infused (1st and 2nd treatment arm, LVPE1, LVPE5, and LVPE9) the following parameters regarding the IVIG dosing will be summarized:

- IVIG infused (yes/no)
- Theoretical IVIG dose (g)
- Infused dose(g)
- Ratio infused dose /theoretical dose
- Number of bottles used

In addition, percentage of plasma exchanges associated with at least one adverse event will also be summarized whether or not related to the procedure and/or study drug.

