5.1.2 Dosage and Treatment Regimen

The six full replacement sessions of the intensive treatment period will be completed in six weeks (one session per week)

The volume of each full plasma exchange will be approximately that of one plasma volume of the patient as calculated from body weight, height and hematocrit (approximately 35-45 mL/kg, corresponding to a volume of 2500-3000 mL).

The 12 low-volume plasma exchange sessions (9 with albumin 20% and 3 with IVIG) of the maintenance treatment period will be completed in 12 months (one session per month).

The volume of each plasmapheresis during the low-volume plasma exchange period will be between 690 and 880 mL of plasma (depending on the patient body weight, following the nomogram for plasma donation used in the USA. (See **Appendix 3**).

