6.1. Definitions and Abbreviations

| Term | Definition |
|----------------------------|--|
| Hct | Hematocrit |
| HSA | Human serum albumin |
| Kit | The Plasmacell-C disposable set after the AC spike, plasma bag, replacement fluid luer, and fistula needle set (including the luer) have been sealed and removed |
| Platelet-Poor Plasma (PPP) | The collected, platelet-poor waste plasma at Day 0 |
| RF | Replacement Fluid |
| VP Time | Venipuncture time; the amount of time between the operator acknowledging that venipuncture is complete and the instrument instructing the operator to disconnect the patient |

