6.2. Equations

$$\text{Kit}_{\text{PRE-WEIGHT}}^{[6]} = 165.8 \text{ g}$$

Kit Residual Volume

$$= [(\text{Kit}_{\text{POST-WEIGHT}} - \text{Kit}_{\text{PRE-WEIGHT}}) \text{ g} \div 1.05 \text{ g/mL}^{[8]}] \text{ mL}$$

Disposable Set and Transfer Set Plasma/RF/AC Line Volumes

$$\begin{aligned} &= \text{AC Line Length}^{[7]} \times \text{AC Tubing Volume per Length}^{[7]} + (\text{Plasma Line Length}^{[7]} + \text{RF Line Length}^{[7]} + \text{RF} \\ &\text{Transfer Set Length}) \times \text{Blood Tubing Volume per Length}^{[7]} \\ &= 84'' \times 0.0196 \text{ mL/inch} + (25'' + 27'' + 12'') \times 0.2043 \text{ mL/inch} \\ &= 14.72 \text{ mL} \end{aligned}$$

Kit RF Volume

$$= [(1/4) * (\text{Kit Residual Volume} - \text{Disposable Set and Transfer Set Plasma/RF/AC Line Volumes})] \text{ mL}$$

Plasma Volume

$$= [(\text{PPP}_{\text{POST-WEIGHT}} - \text{PPP}_{\text{BAG-EMPTY}}) \text{ g} \div 1.027 \text{ g/mL}] \text{ mL}$$

$$\text{PPP}_{\text{BAG-EMPTY}}^{[6]} = 41.87 \text{ g}$$

Replacement Fluid Line and Transfer Set Volume

$$\text{(if filled with fluid)} = [39'' \times 0.2043 \text{ mL/inch}] = 7.97 \text{ mL}$$

$$\text{(if filled with air)} = 0 \text{ mL}$$

$$\text{(if filled with both)} = [19.5'' \times 0.2043 \text{ mL/inch}] = 3.98 \text{ mL}$$

$$\text{RF Cap Weight}^{[6]} = 3.60 \text{ g}$$

Replacement Fluid Volume

$$= [(\text{RF}_{\text{PRE-WEIGHT}} - \text{RF}_{\text{POST-WEIGHT}} - \text{RF Cap Weight}) \text{ g} \div 1.06 \text{ g/mL}^{[9]} - \text{Replacement Fluid Line and Transfer Set Volume} - \text{Kit RF Volume}] \text{ mL}$$

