7.3. Hardware and Software

The instruments will be retained by Grifols after study completion, but the experimental software must be returned to Fenwal, Inc. See TSB-TSB-12560043 for tracking of the return of experimental software.

8. References

1. 931-PLN-01004, Auto-C Plasma Exchange Product Validation Plan
2. TSB-TSB12560043, Install, Test and Configure an Auto-C Instrument with Dory Project Software
3. FQA-01-007, Fenwal Training Process
4. REC-003672, Autopheresis-C Plasma Exchange Protocol Supplemental Operating Instructions
5. 07-19-54-188, Autopheresis-C™ Plasmapheresis System Operator's Manual
6. NB00016-134. "Measurement of Auto-C Plasma Exchange Protocol Kit Tare Weights, Revisited".
7. DWG-0312581824, AUTO-C Plasma Exchange FTX-3900 Disposable Set
8. Trudnowski, RJ and Rico, RC. "Specific Gravity of Blood and Plasma at 4 and 37°C". *Clin Chem* 20 (1974): 615-616.
9. Nugent, RL and Towle, LW. "The Specific Gravity of Synthetic Solutions of Serum Albumin and Serum Globulin". *J Biol Chem* (1933).

9. List of Appendices

- A. Steps for Recording Auto-C Plasma Exchange Procedure Data
- B. Auto-C Plasma Exchange Procedure Data Record
- C. Product Performance Flow Chart
- D. Product Performance Report
- E. Revision History

A. Steps for Recording Auto-C Plasma Exchange Procedure Data

Pre-Procedure:

Before the procedure, record the following on the data sheet in Appendix B:

- Run ID
- Patient Weight

Based on the patient's weight and physician's orders, identify and record the following on the data sheet in Appendix B:

- Plasma Target
- Replacement Fluid (RF) Target
- Type of RF Used

Record the weight of the replacement fluid containers on the data sheet as "RF Weight - Pre" in Appendix B.

Take a fingerstick hematocrit of the patient and record the hematocrit on the data sheet in Appendix B.

During the Procedure:

When entering the replacement fluid infusion states, record any changes to the infusion rate under "Flow Rate during RF Infusion". If no changes are made, the RF Infusion rate is 20 mL/min.

During the procedure, record the following (as applicable) on the data sheet in Appendix B. If there are no notes for the section, write "N/A".

- Patient Adverse Reactions
- Alarm Information (name of alarm and approximate time or state in which it occurred)
- Other Notes

If any product performance issues are observed, see Appendix C.

After the Procedure:

At the end of the procedure, record the following from the display:

- RF Infused

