- Configurable target replacement fluid infusion volume with presets of half doses of 80, 95, 100, and full doses of 160, 190, or 200 mL to correspond with a plasma collection volume of 690, 825, and 880 mL, respectively. An editable option is also available.
- Infusion of programmed volume of replacement fluid via direct infusion of replacement fluid at programmable target infusion rates from 5 to 20 mL/min after collection of the target plasma volume.

CONFIDENTIAL

considers this protocol to be confidential and not subject to disclosure without the express written consent of .

- Ability to infuse IVIG offline from the Aurora instrument using the disposable set interface (Injection Y-Site) for connection to an external infusion pump.

The purpose of this protocol is to investigate the use of the Aurora Plasma Exchange System to return a 20% Albutein[®] (human serum albumin or HSA) solution as the replacement fluid to a patient (if configured for the Albumin protocol). Connection of the Aurora Plasma Exchange Disposable Set to the external infusion pump disposable set via the Injection-Y Site is also a subject of investigation (if configured for the No Albumin protocol). The disposable sets for use during this study are investigational (Product Code FTX3920); they include a fistula needle set attached at a luer, an Injection Y-Site on the patient short line for connection to an external infusion pump, an attached 1000 mL plasma collection container, a spike for connection to an anticoagulant solution, and a luer for connection to a transfer set (aka FleboSet), supplied by Grifols, S.A., that allows for connection of two bottles of 20% Albutein.

3. Materials and Equipment

Materials and equipment that may be used in this study include, but are not limited to:

- SMARTCONNECT Plasma Exchange Disposable Set, Code FTX3920
- Aurora Instrument (Code: 6R4601) with investigational plasma exchange procedure software (software kit product code: 6S9820)
- Grifols Replacement Fluid Transfer Set, *FleboSet[®] Double*
- Sodium Citrate Solution, USP, 500 mL, Code 4B7889Q or equivalent (if configured for 6:100 ratio of Anticoagulant-to-Whole Blood)
- Anticoagulant Citrate Dextrose Solution A (ACD-A), USP, 500mL, Code 4B7898Q or equivalent (Grifols, S.A. branded ACD-A USP 500 mL, REF# 721781) (if configured for 8:100 ratio of Anticoagulant-to-Whole Blood)
- 20% Albutein[®] (Human Serum Albumin, or HSA) , 50 or 100 mL
- RF tubing sealer
- Weight scale

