4.4. Set Up

4.4.1. Plasma Collection Volumes

The target Plasma Collection Volume is chosen at the discretion of a physician in accordance with the clinical protocol. The recommended nomogram is indicated below. Note that plasma collection volumes (plasma plus anticoagulant) shall comply with local regulatory requirements as applicable.

| Patient Weight lbs (kg) | Maximum Plasma Collection Volume (Plasma + Anticoagulant) (mL) |
|----------------------------|---|
| 110-149 (50-67) | 690 |
| 150-174 (68-79) | 825 |
| ≥175 (≥80) | 880 |

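### SAP 7.2.1 reports the Aurora bag contents, which are plasma plus anticoagulant, as plasma exchanged, overstating plasma removed by about 10–13% at a hematocrit of 38%

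*SAP*

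**What the plan says.** SAP 7.2.1 lists the parameters to be summarized for each low-volume plasma exchange. One is "Plasma volume exchanged (calculated as" the post-procedure bag weight less 41.87 g, divided by 1.027 g/mL. No anticoagulant is subtracted and no device is named. Target plasma volume and replacement fluid infused stand in the same list.

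The formula and both constants are those of the "Plasma Volume" equation in the Auto-C protocol (Appendix 3a, 6.2). There the material weighed is defined as "The collected, platelet-poor waste plasma at Day 0", and the tare is referenced to a document titled "Measurement of Auto-C Plasma Exchange Protocol Kit Tare Weights, Revisited".

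The Aurora protocol (Appendix 3b) treats the contents of the bag differently. Its collection nomogram (4.4.1) heads the 690/825/880 mL column as plasma plus anticoagulant and adds: "Note that plasma collection volumes (plasma plus anticoagulant) shall comply with local regulatory requirements as applicable". Its materials list (section 3) gives two configurations: sodium citrate at 6:100, and ACD-A "if configured for 8:100 ratio of Anticoagulant-to-Whole Blood".

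The main protocol (5.1.2) says that each low-volume session "will be between 690 and 880 mL of plasma". It allows either device.

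**The concern.** The SAP label says plasma, but on Aurora the bag that is weighed also holds all the anticoagulant that passed into the plasma line. The reported figure is then too high by the ratio of anticoagulant to plasma in the bag.

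This variable is the SAP's only calculated measure of how much plasma was removed over the 12 maintenance sessions. A reader of the report would take it at face value as exposure. The size of the error also depends on the anticoagulant configuration, so sites using ACD-A and sites using citrate would not be on the same footing.

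**Working it through.** **Inputs from the documents**
- Tare 41.87 g and density 1.027 g/mL: SAP 7.2.1, same as Appendix 3a, 6.2.
- Anticoagulant r = 6 or 8 mL per 100 mL of whole blood: Appendix 3b, section 3.
- Hematocrit H of 38% or more: Appendix 3b, 4.3.1 (Auto-C: Appendix 3a, 4.5).
- Maximum collection volumes 690, 825 and 880 mL: Appendix 3b, 4.4.1.

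**Inputs assumed**
- Any hematocrit other than 38%.
- Anticoagulant of the same density as plasma (tested below).

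**Step 1. What the SAP formula returns.** A bag filled to 880 mL at 1.027 g/mL weighs 880 × 1.027 + 41.87 = 945.63 g. The formula gives (945.63 − 41.87)/1.027 = 880 mL. It returns the whole bag volume, whatever the bag contains.

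**Step 2. Overstatement.** Each 100 mL of blood yields 100(1 − H) mL of plasma and r mL of anticoagulant, so the overstatement is r / [100(1 − H)].
- 6:100, H = 38%: 6/62 = 9.7%
- 8:100, H = 38%: 8/62 = 12.9%

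| Ratio | H = 38% (device floor) | H = 45% (assumed) | H = 50% (assumed) |
|---|---|---|---|
| 6:100 | 9.7% | 10.9% | 12.0% |
| 8:100 | 12.9% | 14.5% | 16.0% |

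**Step 3. Net plasma at H = 38%.** Net = collected × 62/(62 + r).

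| Collected | 6:100 | 8:100 |
|---|---|---|
| 690 mL | 629 mL | 611 mL |
| 825 mL | 752 mL | 731 mL |
| 880 mL | 802 mL | 779 mL |

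**Step 4. Sensitivity**
- *Meaning of the ratio.* If r is counted within 100 mL of already anticoagulated blood, the overstatement is r / [(100 − r)(1 − H)]. At H = 38% this gives 10.3% and 14.0%. At 8:100 and H = 46% it gives 8/(92 × 0.54) = 16.1%; at H = 50%, 17.4%.
- *Lower hematocrit.* If a session were run at 30%, below the device floor, the figures would be 6/70 = 8.6% and 8/70 = 11.4%.
- *Anticoagulant density.* Varying it from 1.00 to 1.03 g/mL moves the result by less than 0.5 percentage point.
- *Tare.* A 10 g error shifts the volume by 10/1.027 = 9.7 mL, which is 1.4% of 690 mL and 1.1% of 880 mL.

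**The case against.** The SAP copies a defined device equation exactly, so there is no slip in its arithmetic. The variable is one of several descriptive session parameters and enters neither co-primary analysis nor the primary safety criterion. On Aurora the target volume is also plasma plus anticoagulant, so target and collected volume already compare like with like. All of this stands. It makes the point one of labelling and interpretation, and it means that correcting the collected figure alone would make fully successful sessions look short of target.

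Four stronger readings are tempting, and the documents do not support them.
- *That 10–16% applies to every low-volume session.* The plus-anticoagulant wording and the ratios appear only in the Aurora protocol. Auto-C lists the same sodium citrate product code and the same 690/825/880 mL nomogram, and Aurora is described as using the same separation technology. A similar error is therefore probable, but the Auto-C ratio is not given.
- *That 16% is a documented upper end.* Only the 38% floor is documented; the upper end needs an assumed hematocrit and the 8:100 configuration.
- *That a replaced-to-removed ratio will be reported too low.* SAP 7.2.1 plans no such ratio. Albumin volume follows a weight nomogram, and the synopsis offers the match between 200 mL of albumin 20% and 880 mL of plasma only as an approximate rationale.
- *That the Aurora tare is wrong.* No document shows that the Aurora bag weighs anything other than 41.87 g. Both sets carry a 1000 mL container. The tare is unverified for Aurora, which is not the same as wrong.

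**Conclusion.** The point holds for Aurora sessions. As written, the SAP reports plasma plus anticoagulant under a plasma label and overstates plasma removed by about 10–13% at a hematocrit of 38%, with the ratio taken per 100 mL of native blood. The figure rises with hematocrit, to about 16% at 8:100 if hematocrit is assumed to be 46–50%, depending on how the ratio is read. For Auto-C the same is probable but cannot be sized from the documents. If its ratio were 6:100, the overstatement would be 9.7–12.0% over hematocrit 38–50%.

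This is a minor reporting error in an exposure variable. It has no bearing on the co-primary results.

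**What to change.** 1. In SAP 7.2.1, report this variable and the matching target as *collected volume (plasma + anticoagulant)*, and state that it is not to be read as plasma removed. This costs two labels and needs no new data.
2. Where the site's anticoagulant ratio and the session hematocrit are available, add a separate net-plasma volume: collected volume × 100(1 − H) / [100(1 − H) + r]. State which reading of the ratio is used and what ratio is assumed for Auto-C.
3. Confirm that 41.87 g applies to the Aurora bag (set FTX3920), or use a device-specific tare.

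Step 2 costs more than a line of code. Both procedure forms accept hemoglobin in place of hematocrit, neither has a field for anticoagulant type or ratio, and weighing was optional on Auto-C. The ratio would have to come from site configuration records. Net plasma cannot be derived for sessions with no bag weight, hematocrit or ratio, and the number of such sessions should be reported.

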7.2.2 Adverse Events

All adverse events will be coded using the Medical Dictionary for Regulatory Activities (MedDRA). Summaries will be presented for all adverse events (overall and by severity), adverse events determined by the investigator to be treatment-related (overall and by severity), serious adverse events, and adverse events causing discontinuation from the study.

The incidence of adverse events will be summarized using descriptive statistics by system organ class and preferred term. Patients are counted only once in each system organ class category, and only once in each preferred term category. Treatment-related adverse event summaries will include adverse events with missing relationship to study drug. For the summaries by severity, patients are counted at the greatest severity. Adverse events missing the flag indicating serious will be excluded from the summary of serious adverse events. In summary tables, AEs will be counted as “Not Related” if the causality with the product was recorded as “Unrelated”; Events will be counted as “Related” if the causality with the product was recorded as “Possibly”, or “Probably,” or “Unlikely”, or if relationship is missing. For the analysis of adverse events, the relationship to the study

	Title: Statistical Analysis Plan
	Project #: IG1002 AMBAR
	Version: Final 1.0 Effective Date: 31July2018
	Protocol Version: Version 5.0 Effective Date: Feb2018

procedure will be used as given in the CRF, regardless of whether or not the adverse event has an onset within 72 hours after the end of the last plasma exchange.

The adverse events will be summarized as follows:

- All AEs by SOC and PT
- All AEs by SOC, PT, and severity
- All AEs by SOC, PT, and causality with product
- Related AEs by SOC and PT
- Related AEs by SOC, PT, and severity
- Related AEs by SOC, PT, and relationship (product, procedure, product + procedure)
- Related AEs by SOC, PT, and product (albumin 5%, albumin 20%, Flebogamma DIF 5%)
- All SAEs by SOC and PT
- Related SAEs by SOC and PT
- SAEs with a fatal outcome by SOC and PT

The relationship to the product will be derived from the most recent plasma exchange.

For AEs which are on the date of the plasma exchange, it is assumed that the AE is during/post exchange, i.e. the AE will be associated to this PE. For the 3 active treatment groups, the derivation of the product will be as follows:

- For FPE1 to FPE6, the product is albumin 5%
- For LVPE 1, LVPE5, or LVPE 9, for the full albumin + IGIV and the half albumin + IVIG treatment arm, the product will be flebogamma DIF 5%
- For LVPE 1, LVPE5, or LVPE9, for the half albumin treatment arm, the product will be albumin 20%
- For all other LVPEs, the product will be albumin 20%.

The related adverse events and related serious adverse events will also be analyzed based on the number of FPEs, FPEs using central access, FPE using peripheral access, and LVPEs. For this analysis, only AEs with an onset time no longer than 72 hours after the end of the most recent plasma exchange will be considered. If the time of onset is missing, or the end time of the plasma exchange/infusion of albumin or IVIG is missing, the start date of the AE must be within 2 days after the date of the most recent plasma exchange. Adverse events with missing relationship will not be considered in this analysis. Each plasma exchange is counted only once in each SOC and only once in each. Adverse events will also be analyzed by product (albumin 5%, albumin 20%, Flebogamma DIF 5%) based on the number of plasma exchanges. The denominator for this analysis is the number of performed plasma exchanges with the specific products.

	Title: Statistical Analysis Plan
	Project #: IG1002 AMBAR
	Version: Final 1.0 Effective Date: 31July2018 Protocol Version: Version 5.0 Effective Date: Feb2018

Listings for deaths, serious adverse events, adverse events leading to discontinuation, MedDRA dictionary terms for adverse event descriptions, and adverse event preferred terms by patient number will be presented. Adverse events associated with plasma exchanges will also be presented.

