9.1.2 Imputability criteria

To analyze the possible relation cause-effect, it will be considered the temporal relationship between drug administration and the AE, possible alternative causes, evolution (complete remission, partial recovery, death and sequelae), persistence or not after drug discontinuation, reappearance with drug re-administration, or the previous knowledge of the event matching up with the known or expected response pattern of the study drug.

The following definitions will be used to establish cause-effect relationships:

Definitive: the adverse event occurs after a reasonable time sequence related to the study drug administration or study procedure, with a known response model, but cannot be explained by the patient clinical condition and other treatments provided, confirmed by improvement after interrupting or diminishing treatment dose, and with relapse after reintroducing treatment.

Probable: the adverse event occurs after a reasonable time sequence related to the study drug administration or study procedure, with a known response model, confirmed by improvement after interrupting treatment, and that cannot be explained by the patient clinical condition or other treatments provided.

Possible: the adverse event occurs after a reasonable time sequence related to the study drug administration or study procedure, with a known response model, but can be explained by the patient clinical condition and other treatments provided.

Unlikely: the adverse event occurs after a reasonable time sequence related to the study drug administration or study procedure, not following a known response model, and that cannot be explained by the patient clinical condition or other treatments provided.

Unrelated: Any other adverse event.

9.1.3 *Expected adverse events*

There are a series of **expected adverse events** attributable to the plasma exchange procedure, with others that are inherent to the replacement fluid used (human albumin). Lastly, other events are a consequence of patient disease or idiosyncrasy.

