10.4 Intermediate Analysis and Stopping Rules

A descriptive analysis is planned once half of the subjects are undergoing low-volume plasma exchanges.

Serious adverse events related to full plasma exchanges (performed during the first six weeks), AEs leading to withdrawal of the study and additional safety measures if required will be monitored by the independent DMC on a regular basis. Special focus will be put on those SAEs considered as related to the therapeutic procedure or Investigational Product(s) by the Principal Investigator as defined in the protocol. Additional common side effects might also be analyzed if significantly higher proportions are found in any of the treatment arms.

Under the following circumstances the independent DMC will recommend to halt the trial partly (stopping a specific treatment arm) temporarily (until modifications to the protocol are completed) or wholly (abandon all study activities):

- If more than 30% of patients undergoing full plasma exchanges experience an SAE as defined by the protocol labeled “Definitively related to the therapeutic procedure” or “Probably related to the therapeutic procedure” or “Possibly related to the therapeutic procedure” and not attributable to the Investigational Products, as judged by the principal investigator.

- If more than 30% of patients undergoing full plasma exchanges experience an SAE as defined by the protocol labeled “Definitively related to the Investigational Product(s)” or “Probably related to the Investigational Product(s)” or “Possibly related to the Investigational Product(s)” and not attributable to the therapeutic procedure or technique of application, as judged by the principal investigator.

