| 13. Relationship to Study Drug  UNRELATED  RELATED ○ Unlikely ○ Possibly ○ Probably ○ Definitely | 14. Relationship to Medical Condition  UNRELATED  RELATED ○ Unlikely ○ Possibly ○ Probably ○ Definitely | 15. Relationship to Other Drugs or Procedures  UNRELATED  RELATED ○ Unlikely ○ Possibly ○ Probably ○ Definitely | 16. Event Outcome  RECOVERED/RESOLVED  RECOVERING/RESOLVING  RECOVERED/RESOLVED WITH SEQUELAE  NOT RECOVERED/NOT RESOLVED  FATAL | | 17. Severity  MILD  MODERATE  SEVERE |

III. STUDY MEDICATION

| | | | | |
|---|--|--|---|---|
| 18. Treatment arm:  Treatment A (Full dose, Albuterin+Flebogamma DIF)  Treatment B (Half dose, Albuterin+Flebogamma DIF)  Treatment C (Half dose, Albuterin only)  Sham group (No therapy) | | | | |
| 19. Product* (*last administered prior event): _____ | | 20. Study period:  Screening  FPE #  IV LVPE #  FV | | |
| 21. Product* started on (DD/MM/YYYY) ____/____/____ | 22. Last date of Study Treatment (prior event) (DD/MM/YYYY) ____/____/____ | 23. Dose | 24. Frequency | 25. Route of administration |
| 26. Lot number | 27. Action taken with study drug due to the event  No change/None  Dose reduced  Interrupted  Discontinued  Other, specify: _____ | | 28. Did event abate after stopping or reducing study treatment?  Yes  No  Not Applicable | 29. Did event reappear after reintroduction of study treatment?  Yes  No  Not Applicable |
| 30. Expiration Date | | | | |

Patient ID: _____ - _____

Initial

Follow-up # _____

IV. OTHER MEDICAL INFORMATION

| | |
|---|--|

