10. **Death Details** (Only for the event which resulted in death): Enter the date of death, check if autopsy and/or death certificated are attached, or leave blank if the subject did not die from THIS event.
11. **Event Onset/Start Date and time:** Record the date and time the first symptoms of the event presented or when the event satisfied one of the serious event criteria, whichever date was earlier.
12. **Event Stop Date and time:** Record the date and time the event resolved. If event is continuing, check the "Ongoing" box.
Event Stop Date is required for all events except cases where subject was lost to follow-up, permanently disabling/incapacitating events, or in cases of death not related to the event. If the event led to the subject's death, then Outcome of this event should be marked "Fatal" and date of death should be entered as the Event Stop Date. If the subject died of another cause while experiencing this adverse event, the Event Stop Date should be left blank, "Ongoing" checked, and Event Outcome of this event should be marked as "Not Recovered/Not Resolved".
If the patient was hospitalized as result of the event, please also complete discharge date in this box.
13. **Relationship to Study Drug:** Check the event's relationship to study drug. This **MUST** be completed. Note that "Unlikely" is classified as potentially related to study drug.

Serious Adverse Event (SAE) Report Completion Guidelines

14. **Relationship to Medical Condition:** Check the event's relationship to patient's medical condition.
15. **Relationship to Other Drugs or Procedures:** Check the event's relationship to other drugs or study procedures.
16. **Event Outcome:** Check the appropriate outcome of this event. If the subject's death was related to the event, then Outcome should be marked "Fatal." If the subject died from another cause while experiencing this event, DO NOT mark "Fatal" as an outcome, but check "Not Recovered/Not Resolved".
17. **Severity:** Check the appropriate severity for this event.
18. **Treatment arm:** please indicate randomization arm for the subject.
19. **Product* (*last administered prior event):** please indicate the study product that the patient last received prior presenting the serious adverse event.

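### SAP 7.2.2 places the highest product-causality level (Definitive/Definitely) in neither Related nor Not Related

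*SAP*

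**What the plan says.** SAP 7.2.2 gives one counting rule for its summary tables. An event is Not Related if its product causality is recorded as Unrelated. For the other side: "Events will be counted as “Related” if the causality with the product was recorded as “Possibly”, or “Probably,” or “Unlikely”, or if relationship is missing".

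The causality scale itself is in Protocol 9.1.2: Definitive, Probable, Possible, Unlikely and Unrelated, each applying to the study drug or the study procedure. The top level opens "Definitive: the adverse event occurs after a reasonable time sequence related to the study drug administration or study procedure" and is restrictive: among other conditions it requires improvement when treatment is interrupted or the dose is reduced, "and with relapse after reintroducing treatment". The SAE form in Appendix 4, box 13, offers Unrelated or "RELATED ○ Unlikely ○ Possibly ○ Probably ○ Definitely". Its completion guideline adds: "Note that 'Unlikely' is classified as potentially related to study drug". Protocol 10.4 uses the top level too, as in "Definitively related to the therapeutic procedure", with a parallel wording for the product.

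The opening of SAP 7.2.2 promises summaries of "adverse events determined by the investigator to be treatment-related (overall and by severity"). The section then lists ten tables. Among them are "All AEs by SOC, PT, and causality with product", a table of related events split by whether the relation is to the product, the procedure or both, and a table of related events by individual product. Relationship to the procedure is to be taken from the CRF.

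**The concern.** A causality rule should place every recordable level on one side or the other. This one lists four of the protocol's five levels plus missing, and the one left out is the strongest. A programmer who codes the list will put Unlikely and missing events in the Related tables and leave Definitive events out of them, and out of the Not Related group as well. A reader of the Related AE and Related SAE tables would not know that the clearest cases are absent.

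A second, smaller gap lies beside it. The rule speaks only of the product, while one planned table has a level for events related to the procedure. The SAP says where procedure causality comes from, but not which of its levels count as related.

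**Working it through.** No figure in the plan is at issue, so the check sets the texts side by side.

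**Step 1: map the levels.**

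| Protocol 9.1.2 | SAE form, box 13 | SAP 7.2.2 (product) |
|---|---|---|
| Definitive | Definitely (under Related) | not assigned |
| Probable | Probably (under Related) | Related |
| Possible | Possibly (under Related) | Related |
| Unlikely | Unlikely (under Related) | Related |
| Unrelated | Unrelated | Not Related |
| missing | – | Related |

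Protocol levels: 5. Levels assigned by the SAP: 4. Unassigned: 5 − 4 = 1. On the SAE form, the Related branch has 4 levels and the SAP keeps 3, so again 4 − 3 = 1 is lost. Counting Unlikely as Related agrees with the SAE guideline and is not the problem. No other part of the SAP assigns the top level.

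**Step 2: count the tables exposed.** Of the ten summaries in SAP 7.2.2, four AE tables are limited to Related events (by SOC and PT; by severity; by relationship; by product), and so is one SAE table: 4 + 1 = 5 of 10. The table by causality with product would be a sixth (5 + 1 = 6), but only if it is built from the two collapsed categories. If it shows every recorded level, nothing is lost there.

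**Step 3: look at procedure causality.** Take an event recorded as Unrelated to the product and Probable for the procedure.

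- If the product rule is the filter for the relationship table, the event is Not Related and cannot enter the procedure level.
- If product and procedure are two separate axes, the event enters the procedure level, provided the SAP says that Probable counts as related on that axis. It does not say so for any procedure level.

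The gap is therefore an unstated grouping on the procedure axis, in 1 of the 3 levels of one table (product, procedure, both).

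**Step 4: size.** The documents give no share of events graded Definitive or related to the procedure only. Definitive requires recurrence on re-exposure, so such events may be few. On the other hand, up to 6 weekly and 12 monthly sessions make re-exposure part of the design. No number can be put on it.

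**The case against.** The strongest reply is that the intent is plain. Only Unrelated is assigned to Not Related, even Unlikely and missing count as Related, and the section's opening speaks of events the investigator judged treatment-related. Nobody would set out to drop the surest cases. That is very likely right, and the omission looks like an oversight in the wording. But the intent is stated in general terms and the counting rule as an explicit list, and the list is what gets programmed.

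It can also be said that all safety analyses are descriptive (SAP 9.2.3), that the events remain in the all-AE and all-SAE tables, and that the CRF, which is not among the documents, may not offer the top level. The first two points stand and limit the consequence. The third cannot be excluded, but the protocol defines the level, the SAE form offers it and the stopping rules use it.

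On the procedure side the objection is stronger. A reader might infer that the SAP ignores procedure causality, or that the procedure level of the relationship table must come out empty. The documents do not support that. The sentence governs causality with the product, the next one takes procedure relationship from the CRF, and a table with separate product and procedure levels fits a two-axis reading. What survives is only that no grouping of levels is given for the procedure.

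**Conclusion.** The point holds for product causality: the top level has no place in the rule, and the Related AE and Related SAE tables, taken literally, would omit it. The scope is one of five protocol levels and five of ten listed summaries, with a sixth conditional on how it is built. The number of events is unknown. The conclusion assumes that the CRF offers the top level, as the protocol scale and, for SAEs, the SAE form indicate.

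The procedure part is a request for a missing definition, not an error in a result.

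A reader might also infer that the primary safety criterion is understated. It is not governed by this sentence: SAP 7.2 and 7.2.1 base it on events possibly related to the study procedure. Efficacy conclusions are untouched.

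The correction should be made because it is cheap and because these tables are where related harm is read. It does not threaten the trial.

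**What to change.** In SAP 7.2.2, state that Related to product means Unlikely, Possibly, Probably, Definitely/Definitive or missing, and that Not Related to product means Unrelated.

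Separately, for the table split by product, procedure or both, state that procedure relatedness is judged on its own CRF field, and list which levels of that field count as related and how a missing value is handled. An event Unrelated to the product can then enter the procedure level. This grouping should be chosen explicitly and not copied from the product rule. The SAE guideline's note on Unlikely refers to the study drug, the SAP's missing-value rules are written for study drug or product, and the procedure stopping rule in Protocol 10.4 names only the top three levels.

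Keep the by-product and causality-with-product tables on product causality alone. A single definition of related to product or procedure would do damage there: the by-product table takes the product from the most recent exchange, so a catheter complication judged Unrelated to the product could be listed under albumin 5%. Leave as it stands the existing exclusion of events with missing relationship from the analysis per plasma exchange.

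The cost is a sentence or two in the SAP and a small programming change. Adding the top level can only raise, never lower, the counts related to product. The effect of the procedure grouping depends on the levels chosen and cannot be predicted from the documents.
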